IRB Quality Initiative <[contact]>

RE: [name] 827461 QI Letter

To: [name]; [contact]'

Cc: [name]; [name]

You forwarded this message on 5/30/2019 2:09 PM.

[Bing Maps](#)

[+ Get more apps](#)

Hi [name],

The proposed changes do not change the QI determination. The original letter still applies.

Institutional Review Board  
University of Pennsylvania  
Office of Regulatory Affairs  
[name]  
[name]  
[name]  
[www.upenn.edu/IRB](http://www.upenn.edu/IRB)

---

**From:** [name] <[[contact]](mailto:[contact])>

**Sent:** Thursday, January 31, 2019 9:50 AM

**To:** [contact]' <[[contact]](mailto:[contact])>

**Cc:** [name] <[[contact]](mailto:[contact])>; [name] <[[contact]](mailto:[contact])>

**Subject:** RE: [name] 827461 QI Letter

Hi,

I'm writing in reference to our QI Project 827461.

Our project began by collecting information about post-op medication use by telephone, and our current program engages patients after their procedure through a text message conversation to learn about their pain and use of prescribed medications.

We would like to understand the most efficient approach in gathering this data. Currently, patients receive a set of text message questions and our team awaits responses. As an alternative we have learned that we can send patients a single text message with a link to a web-based survey which would ask the same question set, but allow for patients to click through the questions rather than the text message exchange.

We would like to include this survey link as a method to collect information for this project. We would compare the methods to see which are the most efficient. This may be completed as two groups – one receiving text conversations and one receiving the text link to an online survey containing the questions. The results of the comparison could possibly lead to a publication.

Please let me know if this still qualifies as QI.

Thank you so much,  
[name]

This worksheet is a guide to help the submitter and the IRB to determine if an activity is quality assurance/quality improvement or is human research as defined by the Health and Human Services (HHS) or Food and Drug Administration (FDA). Once completed, please email the form to [[contact]](mailto:[contact]). The IRB will contact you with the results of their review and may request additional information to assist with their determination.

### QI/QA Assessment Process

In order for the IRB to assess whether your project meets the definition of human subjects research requiring IRB review or may qualify as a quality improvement/assurance activity, please provide the following information:

1. Provide a summary of the purpose and procedures of the proposed project. In your summary, please address:
  - the project question or hypothesis that you are planning to evaluate
  - the project design

- any interaction or intervention with humans
- a description of the methods that will be used and whether they are standard or untested
- whether identifiable data from individuals will be used (if so, identify the source of the data and how the data will be obtained or accessed).
- a description of how the collected data will be used- (example, prepare a report for operational leaders, publish the findings, etc).

At UPHS, patients who are treated for acute fractures and/or undergo orthopedic surgical procedures and have no contraindications to narcotics are routinely prescribed opioids following the procedure and given a prescription for oral opioids prior to discharge home. The number of pills prescribed upon discharge varies from provider to provider, ranging from 30-90 pills. This project would address if this number of pills is in accordance with the number of pills that patients require, and how patients are storing or disposing of unused pills. The purpose of the research would be to better understand the amount of opioid pain medication actually required by patients following different orthopedic procedures, with an aim to better meet post-treatment pain requirements and reduce the risk for opioid diversion in the West Philadelphia community. An additional aim of this project is to see if texting patients can be an efficient and effective method for collecting this information as part of clinical standard of care.

This project will be conducted with [name] in the Emergency Medicine Department, who as part of the Nudge Unit, "aims to leverage insights from behavioral sciences, principally behavioral economics, to design and test interventions that steer providers and patients toward better decisions to improve health care delivery and outcomes."

This project would include all Orthopedic patients or ED patients treated for acute fracture discharged from the University of Pennsylvania Health System with an opioid prescription. Patients will be contacted via phone call, text message, or text to an online survey and they will consent to receive text message communications as part of their general surgical consent process.

Patients would be contacted via phone or text message 3-8 days following their orthopedic procedure. The following template would be used for telephone calls:

Hi, my name is [investigator's name] and I am calling from the University of Pennsylvania. I am calling to check in with you to see how you are doing after your recent orthopedic procedure. It looks like you had your knee arthroscopy on (date) with [name], so we just wanted to call and see how you are feeling in terms of pain levels and ask if you are having any concerns that you would like to make your doctor aware of. Do you have a few minutes to go over some questions about how you are feeling?

1. How are you feeling?
2. How many days after your procedure did your pain substantially improve (i.e. wisdom tooth removal- pain lasted for 2 weeks, but the most intense pain lasted 3 days)?
3. Since you have been home, on a scale of 1-10, with 1 being not at all able and 10 being extremely able, how have you been able to manage your pain at home?
4. What types of things have you been doing to manage your pain?
5. Have you used any methods such as ice or NSAIDS like Tylenol or Motrin to help with your pain?
6. It looks like you were prescribed (RX) for your pain. Have you been using this medication?
7. Are you still using it?
8. How many pills do you have remaining?
9. Do you plan on using the remainder of the medication?
10. Do you plan on using any other methods of pain relief, such as (ice, NSAIDS like Tylenol or Motrin, or any different method provided above if given)?
11. Have you had any concerns after your procedure?
12. Did the physician/medical team educate you about your medications and go over the directions for using them?

13. Is there anything you would like to relay to the medical team about how you are feeling?

After completing the interview, the investigator will provide information to the patients about methods for safely disposing any unused medication, including: (b) finding a local "buy back" program, or (c) flushing the unused medication down the toilet (per FDA recommendations).

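### Storage and disposal of unused pills are part of the project question, but no script item, listed chart variable or planned analysis records them

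*Combined protocol and SAP*

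**What the plan says.** Item 1 of the QI/QA Assessment Process names two things the project will address: whether the quantity prescribed matches what patients need, and "how patients are storing or disposing of unused pills". The purpose sentence that follows includes the aim to "reduce the risk for opioid diversion in the West Philadelphia community".

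The data come from a 13-question telephone script. Three questions bear on the fate of the pills:
- Question 6: "Have you been using this medication"
- Question 8: "How many pills do you have remaining"
- Question 9: "Do you plan on using the remainder of the medication"

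Disposal itself appears only after the script, as something told to the patient: "After completing the interview, the investigator will provide information to the patients about methods for safely disposing any unused medication".

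The text-message version sends the script's questions, and the second contact repeats them. The project team's email to the IRB, at the front of the document, describes the survey arm as "a link to a web-based survey which would ask the same question set, but allow for patients to click through the questions". On timing, "Patients would be contacted via phone or text message 3-8 days following their orthopedic procedure", with a second contact 5 to 8 days after the first for patients who report that they are still using opioids.

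The analysis paragraph plans a tabulation of tablets left at 1 and 2 weeks, a comparison of the characteristics of patients with none left, and the proportions whose needs would be met by default quantities of 20, 30, 40, 50 and 60.

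**The concern.** A stated part of the project question has no data source and no analysis. If the plan is followed exactly, the team will finish without knowing where leftover pills are kept, whether any were disposed of, or by what method. That matters because one stated aim is to lower the risk of diversion.

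There is also a possible side effect on the pill counts. Question 8 asks how many pills remain, not how many were taken. A patient who disposed of the remainder therefore gives the same answer to that question as one who took everything.

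**Working it through.** The plan gives no figure on this point to reproduce. The check sets the stated question against everything the plan collects or analyses.

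**Coverage of storage place, disposal and method**
- Script questions 1 to 3: general state, time to improvement, ability to manage pain. Not covered.
- Questions 4, 5 and 10: methods of pain relief. Not covered.
- Questions 6 and 7: whether the prescribed drug was used and is still used. Not covered.
- Questions 8 and 9: number remaining and intention to use them. Partly relevant (see below).
- Questions 11 to 13: concerns, medication education, messages to the team. Not covered; a remark about storage or disposal would be incidental and could not support a proportion.
- Count: 0 of 13 questions. Text, web survey and second contact use the same questions, so they add none.
- Listed chart variables (age, parity, procedural complications, opioid use before discharge): 0 of 4. The list may not be exhaustive, but nothing in the text suggests that storage or disposal would come from the record.
- Planned analyses: 0 of 3.

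**What questions 8 and 9 do give.** A count above 0 at question 8 with no at question 9 identifies a patient holding pills without a plan to use them. Place, disposal and method remain unknown. None of the three analyses tabulates question 9, so even this partial information has no planned use.

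**Possible effect on pill counts.** Take 30 pills dispensed, the low end of the stated 30 to 90. The taken and disposed figures are illustrative.
- 10 taken, 20 disposed of: remaining = 30 − 10 − 20 = 0; question 6 yes.
- 30 taken: remaining = 30 − 30 = 0; question 6 yes.
- 0 taken, 30 disposed of: remaining = 30 − 0 − 30 = 0; question 6 no, so this patient could be told apart if question 6 is used.

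The first two patients give identical answers on questions 6 and 8, and both fall in the group with none left. If use is also derived as dispensed minus remaining (an assumption; the text gives no derivation), the first patient counts as 30 − 0 = 30 used. That exceeds the 20-pill default, although true use was 10, which is within it. The documents give no basis for estimating how many such patients there are.

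**Timing.** First contact is at days 3 to 8. A second contact 5 to 8 days later falls between day 3 + 5 = 8 and day 8 + 8 = 16. The plan gives two conditions for second-round data. The outreach paragraph requires continued opioid use; the analysis paragraph ties the 2-week count to pain still being reported at the 1-week call. These are different groups.

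**The case against.** The strongest reply is about weight. Storage and disposal occupy one clause of one sentence. The intended uses of the data (a new discharge order, and the effect of the New Jersey law) rest on pill quantities, and the comparison put to the IRB concerns which contact method is more efficient. None of these needs storage or disposal data, and deleting the clause would remove the inconsistency. This stands as a limit on the consequences and as a reason to treat deletion as a full alternative. It does not remove the mismatch.

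A second reply is that questions 8 and 9 already capture the information closest to diversion: pills held with no plan to use them. That also stands, so a reader who infers that nothing about unused pills is collected goes too far.

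A third concerns the pill counts. A reader might infer that the quantity analyses are biased or invalid. The documents do not support that. The problem needs a patient who took some pills and had disposed of all the rest by the time of contact. At first contact that is before the project's own disposal information, and the frequency is unknown. The error at the 20-pill default also depends on an assumed derivation of use. The example shows a possibility, not a magnitude.

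Finally, a reader might infer that only continuing users can have second-round data. The outreach paragraph says so, but the analysis paragraph uses a different condition.

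**Conclusion.** The point holds as a mismatch between the stated question and the data. Storage place, disposal and method are covered by 0 of 13 script questions, 0 of 4 listed chart variables and 0 of 3 planned analyses. That part of the question cannot be answered beyond identifying patients who hold pills they do not plan to use. It should be corrected, but it does not threaten the pill-quantity analyses, which can be run as planned. The misclassification of partial users who disposed of the rest is secondary and hypothetical.

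The conclusion rests on the script, chart list and analysis paragraph being complete as they appear. Part of the document was not available for this check, but these sections read continuously.

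**What to change.** Choose one of two equal options.

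**Option 1: collect the data.** After question 9 and before the disposal information, add closed items, identical in telephone, text and web survey:
- (a) Where the remaining pills are kept, if question 8 is above 0.
- (b) What has been done with any unused pills, asked of everyone, including those with 0 remaining, so that patients who disposed of pills can be identified. If question 8 is above 0 and question 9 is no, also ask what is planned, recorded separately.

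Report storage separately for patients who do not plan to use the remainder (unused pills) and those who do (current supply); pooling them would not answer a question about unused pills. Report disposal among patients who hold unused pills or who report disposal. Report second-contact answers separately, because those patients may already have received the disposal information, and reconcile the two second-contact conditions. Start the items on the same date in the text and survey groups.

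Cost per contact:
- 0 remaining: 1 extra response (1/13 = 8%).
- Pills remaining and a plan to use them: 2 extra (2/13 = 15%).
- Pills remaining and no plan to use them: 3 extra (3/13 = 23%).
- A patient contacted twice: up to 2 × 3 = 6 extra.

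One descriptive table is added. The burden may differ between message exchanges and survey clicks and could affect the efficiency comparison, so the change should be recorded there. The email to the IRB shows that collection had already begun, so patients contacted earlier will have no data on these items; the report should say so. A check that the QI determination still applies may be needed, as was made for the survey link.

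**Option 2: remove the storage and disposal clause** from the project question. This costs one line and makes the question match the data, but gives up that part of it.

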Please Note: By submitting your proposed project for a QA/QI determination you are certifying that if the project is established to qualify as QA/QI, you and your Department would be comfortable with the following statement in any publications regarding this project: "This project was reviewed and determined to qualify as quality improvement by the University of Pennsylvania's Institutional Review Board."
